**Figure 1: Overall study design****3.2. Number of centers and patients**

In the screening period, an approximate number of 60 patients will be included.

In the treatment period:

- Cohort A: at least 13 patients will be enrolled to allow sufficient number of patients evaluable for safety, efficacy and immunological analyses.
- Cohort B: number of patients included at the time of full accrual in Cohort A with a maximum of 10 patients.

The study will be a multicenter one with 3 centers from Mayo Clinic in the US and 3 centers in France.

**3.3. Discussion of Study Design**

The first-in-man study of TG4050 is designed as a phase I trial to evaluate primarily the safety of TG4050 administered alone in stage IIIC or stage IV HGSC patients with an asymptomatic relapse. This clinical setting will also allow the evaluation of serum CA-125 doubling time and half-life as appropriate, time to normalization, response according to GCIG criteria and immune response to TG4050.

The screening period will run from at least 6 months after completion of first-line platinum-based chemotherapy to the documentation of an asymptomatic relapse. Patients who achieved a complete response as demonstrated by non-evidence of disease on the last CT-scan and normal CA-125 can be enrolled. Archived tumor tissue collected at the time of abdominal surgery and/or at diagnosis will be used for TSAs identification and subsequent individualized TG4050 MVA construct manufacturing. If the patient has received neoadjuvant chemotherapy, the tumor tissue must be obtained from a core needle biopsy (18G minimum) performed at diagnosis.

The treatment period will run from the documentation of asymptomatic relapse until a total of 20 injections of TG4050 unless disease progression justifying initiation of further treatment, unacceptable toxicity including occurrence of a dose-limiting toxicity or patient withdrawal for any reason whichever occurs first.

A safety run-in phase will be conducted in the first 3 treated patients from Cohort A or B who will be observed during the 6 weeks after TG4050 first dose. For patients presenting with a biochemical relapse detected on the basis of raised serum CA-125 concentration alone, no survival benefit has been demonstrated from early chemotherapy treatment compared to delayed treatment on the basis of clinical relapse ([Rustin G.J. et al., 2010](#)). The lead time between CA-125 increase and clinical recurrence was shown to be 4.8 months on average which will allow to investigate the tolerance of TG4050. This time period will allow to capture immune response to TG4050 and its possible impact on CA-125 doubling time and half-life as appropriate, time to normalization and response. In current practice, second-line treatment is rarely initiated when relapse is asymptomatic, even in the presence of small measurable lesions, and the patient is usually followed with a CT-scan performed 2 months later. National Comprehensive Cancer Network guidelines endorse delaying treatment until clinical relapse.

This patient population may benefit from study treatment and will be evaluated separately in Cohort B.

### 3.4. Dose and schedule selection

Dose and schedule for TG4050 administration have been selected on the basis on the broad clinical experience gathered on TG4010, an MVA carrying coding sequences for the human MUC1 antigen and human interleukin 2 also developed by Transgene. As of end 2018 a total of 354 cancer patients, mostly non-small cell lung cancer (NSCLC) patients, received SC injections of TG4010 at a dose of  $1 \times 10^8$  PFU weekly for 6 weeks followed by every 3 weeks administrations.

- Rationale for the route of administration

In pre-clinical experiments, SC and IM administrations of research grade TG4010 resulted in similar anti-tumoral activity as measured by survival in the RMA-MUC1 prophylactic mouse model. This finding was repeated with the other Transgene MVA-based gene therapy products. The SC route has been chosen from phase II studies of TG4010 and other MVA-based products as it appears a more effective route of administration to initiate an immune reaction which is the expected mechanism of action for Transgene MVA-based products. It has been demonstrated as a safe and immunogenic route in the clinic with MVA-based products.

- Rationale for the dose and regimen:

In TG4010 development, phase II clinical trials were conducted testing different doses and schedules of administration of the study drug.

The dose of  $1 \times 10^8$  PFU was selected based on its good tolerance and immunogenicity.

With its design targeting patient specific neoantigens, TG4050 products should target more immunogenic antigens than the ones targeted by MVA-based products already tested in clinic by Transgene. It is envisaged that a critical dose threshold needs to be reached to achieve an immunogenic response disregarding the nature and immunogenicity of the patient specific antigens carried by the MVA vector. This was consolidated by a pre-clinical experiment in HLA-A2 mice who received different doses of MVA constructs representative of TG4050 and showed response with no dose-response effect.

Sticking with a dose of  $1 \times 10^8$  PFU which allowed immunogenic response with an MVA-based product carrying a weak antigen sequence (i.e.: MUC1 antigen for TG4010) should then be relevant for TG4050. The high specificity of TG4050 antigens to the human tumor should prevent from autoimmune reaction.

In prostate cancer patients the change in PSA doubling time from before treatment to during treatment was statistically significant in patients who received TG4010 weekly for 6 weeks then every 3 weeks while this change was not significant in those who received TG4010 every 3 weeks. Therefore, this treatment regimen was used in all subsequent studies.

- Rationale for repeated administrations scheme:

Therapeutic vaccines do not directly target the tumor but they rather aim at activating and amplifying immune reactions against the tumor. Immune responses often take time to develop and can potentially be enhanced by continued booster vaccinations. Then a repeated schedule of administration was selected for TG4010 as well as the other Transgene MVA-based products and is also applied to TG4050 in the clinic. This repeated dose study regimen was shown to be

well tolerated, grade 1 or 2 injection site reactions being the most frequent Adverse Events (AEs). Importantly this regimen of TG4010 in combination with standard chemotherapy was shown to improve patient outcome in a randomized placebo-controlled, double-blind phase 2 study comparing the combination with chemotherapy and placebo in 222 first-line NSCLC patients (Quoix E. *et al.*, 2016). Consistent with repeated injections of TG4010, development of CD8+ T cell response to MVA-specific epitopes were observed at different timepoints and more frequently in the TG4010 arm in comparison to the placebo arm in this phase 2 clinical trial (Tosch C. *et al.*, 2017). Interest of repeated administrations was also evidenced with MVA-based products not developed by Transgene. For instance, CD4+ and CD8+ T-cell responses to MVA or Dryvax were reported in subjects vaccinated with TBC-MVA and responses were augmented after three doses of MVA compared to one dose (Parrino J. *et al.*, 2007).

From an immunologic perspective, there is a theoretical possibility of T cell cross-reactivity with repeated administrations of TG4050. This potential risk was previously monitored in TG4010 clinical trials assessing repeated administrations of  $1 \times 10^8$  PFU through auto-immunity parameters assessment (e.g. anti-DNA antibodies, anti-nuclear antibodies, thyroid stimulating hormone, anti-thyroperoxidase antibodies). While some of these antibodies increased slightly during study compared to pre-treatment level, it was never considered clinically significant by the investigators. There was also no clinical evidence of auto-immunity to glandular mucins reported (Sjogren's syndrome). No further autoimmunity clinical issue is expected with TG4050 as it targets mutations of patient specific tumor antigen and it has a different mechanism of action from checkpoint blockade. Overall the good tolerance and the efficacy of the proposed TG4050 regimen have been established for an MVA-based product developed by Transgene.

TG4050 will be administered at  $1 \times 10^8$  PFU by subcutaneous (SC) injections weekly for the first 6 weeks and then every 3 weeks up to a total of 20 injections unless disease progression justifying initiation of further treatment, unacceptable toxicity including occurrence of a dose-limiting toxicity, or patient withdrawal for any reason, whichever occurs first.

## 4. STUDY POPULATION

### 4.1. Inclusion criteria

#### Screening period

1. Signed written informed consent in accordance to ICH-GCP and national/local regulation before any protocol-related procedures that are not part of normal patient care.
2. Female patients  $\geq 18$  years of age
3. Histologically confirmed high grade, stage IIIC or stage IV (FIGO staging) serous ovarian, fallopian or primary peritoneal carcinoma with abnormal CA-125 at diagnosis.
4. Patients who have undergone primary debulking surgery or interval debulking surgery and completed a total of at least 5 cycles of taxane-platinum combination. Note: patients may have received concurrent or maintenance bevacizumab or a PARP inhibitor
5. Patients must have achieved a complete response to therapy, as demonstrated by no residual disease on most recent CT scan and normal CA-125.
6. Patient who remains disease free at least 6 months from last prior dose of cytotoxic chemotherapy (maintenance therapy with bevacizumab or a PARP inhibitor is allowed).

7. Available tumor tissue, banked from previous abdominal debulking surgery and/or from a core needle biopsy performed at diagnosis if the patient received neoadjuvant chemotherapy, and peripheral samples to be submitted to complete exome and transcriptome sequencing.

**Treatment period:**

8. Eastern Cooperative Oncology Group (ECOG) performance status of 0 or 1 at treatment period initiation.
9. Patients who have developed an asymptomatic relapse as defined by:
  - Cohort A: CA-125  $\geq$  2 times Upper Limit of Normal (ULN) on 2 occasions at least 1 week apart (GCIG criteria) or low volume radiological disease and CA-125  $>$  ULN. Low volume radiological disease is defined as radiologically visible disease excluding intra-hepatic or intra-splenic metastases, ascites or pleural effusion thought to require drainage
  - Cohort B: patient asymptomatic with measurable disease excluding intra-hepatic or splenic metastases, ascites or pleural effusion thought to require drainage, whatever serum CA-125 level and for whom further treatment is not planned within 2 months. Longest diameter of measurable lesion on CT-scan must not exceed 2 cm for non-nodal lesions and 2.5 cm in short axis for nodal lesions
10. Adequate hematological, hepatic and renal functions:
  - Hemoglobin  $\geq$  9.0 g/dL
  - Neutrophils count  $\geq$  1.5  $\times$  10^9/L
  - Lymphocytes count  $\geq$  0.9  $\times$  10^9/L
  - Platelets count  $\geq$  100  $\times$  10^9/L
  - Total bilirubin  $\leq$  1.5  $\times$  ULN (except for patients with Gilbert's syndrome)
  - Aspartate aminotransferase (AST)  $\leq$  2.5  $\times$  ULN
  - Calculated creatinine clearance  $\geq$  45 mL/min using the Cockcroft-Gault formula or  $\geq$  45 mL/min/1.73m^2 using other methods

Note: for Cockcroft-Gault formula:

$$\text{Creatinine clearance for females (mL/min)} = \frac{(140 - \text{age})(\text{weight in kg})(0.85)}{(72)(\text{serum creatinine in mg/dL})}$$

$$\text{Creatinine clearance for females (mL/min)} = \frac{(140 - \text{age})(\text{weight in kg})(1.04)}{(\text{serum creatinine in } \mu\text{mol/L})}$$

11. Patients who received standard maintenance therapy will stop before initiation of TG4050 administration. A free interval of at least 30 days will be respected before first dosing of TG4050 except for PARP inhibitors (at least 14 days).

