### Treatment period

7. Measurable disease associated with the appearance of symptoms justifying initiation of further treatment.
8. Major surgery within 4 weeks prior to treatment start
9. Treatment with another investigational agent within 30 days prior to TG4050 treatment initiation.
10. Patients under chronic treatment with systemic corticosteroids or other immunosuppressive drugs for a period of at least 4 weeks and whose treatment was not stopped 2 weeks prior to TG4050 treatment initiation planned date, with the exception of patients with adrenal insufficiency who may continue corticosteroids at physiological replacement dose, equivalent to  $\leq$  10 mg prednisone daily. Steroids with no or minimal systemic effect (topical, inhalation) are allowed.
11. Vaccination for the prevention of infectious diseases with a live vaccine during the four-week period prior to TG4050 treatment initiation planned date. Furthermore, patients should not receive any live vaccine during the period of study treatment administration.
12. Patient with any underlying medical condition that, in the opinion of the investigator, could make the patient inappropriate for entry into this study or interfere significantly with the proper assessment of safety or toxicity of the study treatment.
13. Uncontrolled intercurrent illness including, but not limited to, ongoing or active infection, symptomatic congestive heart failure, unstable angina pectoris, cardiac arrhythmia, or psychiatric illness/social situations that would limit compliance with study requirements.
14. History of myocardial infarction  $\leq$  6 months.

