#### 9.1.2. Treatment period

Patients will be enrolled in separate cohorts at the time of treatment initiation according to:

- Cohort A: patients develop an asymptomatic relapse defined on the basis of progressive serial elevations of serum CA-125 (GCIG criteria) or documentation of low volume radiological disease with CA-125 > Upper Limit of Normal (ULN). Low volume radiological disease is defined as radiologically visible disease excluding intra-hepatic or intra-splenic metastases, ascites or pleural effusion thought to require drainage.
- Cohort B: patients develop an asymptomatic relapse with measurable disease excluding intra-hepatic or splenic metastases, ascites or pleural effusion thought to require drainage, whatever serum CA-125 level and for whom further treatment is not planned within 2 months. Longest diameter on CT-scan must not exceed 2 cm for non-nodal lesions and 2.5 cm in the short axis for nodal lesions.

Safety Analysis Set (SAF): all patients included and who received at least one dose of TG4050 will be included in the SAF. This is the primary dataset for safety analyses.

Evaluable Safety Set (ESAF): first 3 patients in SAF who completed the first 6 weeks of treatment or discontinued due to a DLT. Patients who are not evaluable for safety analysis during the run-in phase, or who are withdrawn for other reasons than toxicity, will be replaced.

Evaluable Per-Protocol Set (EPP): all included patients in each cohort without any major protocol deviation who received at least the 6 first weekly injections of TG4050 corresponding to the treatment induction phase and have at least two baseline and two post-baseline evaluations of CA-125 and one baseline and one post-baseline CT-scan or MRI.

Modified Evaluable Per-Protocol (mEPP): patients from EPP in each cohort who are evaluable for immune response meaning at least one pre-dose evaluation and one post-baseline evaluation.

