### 9.3.2. Secondary endpoints

- Failure to provide rate: percentage of patients for whom TG4050 cannot be provided and the reason for not being able to provide the vaccine will be recorded.
- Failure to treat rate: percentage of patients who cannot receive TG4050 and the reason that prevent patient from being treated.
- CA-125 doubling time and half-life as appropriate
- Time to normalization of CA-125
- Response according to GCIC criteria
- Time to measurable relapse in Cohort A and Time to progression in Cohort B per RECIST 1.1
- Tumor response according to RECIST 1.1

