## **4 STUDY DURATION**

The study started in Q4 2019. The study was stopped due to low inclusion rate in October 2024 with 6 patients treated.

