## **6 DEFINITION OF THE POPULATIONS TO BE ANALYSED**

### **6.1 Populations**

- Screening period:**

All patients having signed the ICF will be considered as screened patients and included in the screening population (SCR). The percentage of patients not treated afterwards and the corresponding reason, will be analyzed.

Screening population (SCR): all patients who have signed the ICF.

- **Treatment period:**

Safety Analysis Set (SAF): all patients who received at least one dose of TG4050 will be included in the SAF. This is the primary dataset for safety analyses.

Evaluable Safety Set (ESAF): first 3 patients who completed the first 6 weeks of treatment or discontinued before due to the occurrence of a DLT. Patients who are not evaluable for safety analysis during the run-in phase or who are withdrawn for other reasons than toxicity, will be replaced.

Evaluable Per-Protocol Set (EPP): all treated patients without any major protocol deviation who received at least 6 injections of TG4050 corresponding to the treatment induction phase.

[figure not shown]
Modified Evaluable Per-Protocol (mEPP): patients from EPP who are evaluable for immune response meaning at least one pre-dose evaluation and one post-dose evaluation.

Given the small number of patients, this population won't be used.

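### SAP Appendix 1 eligibility codes do not match the protocol: applied as written, every Cohort B patient becomes a major deviator

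*Protocol*

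**What the plan says.** **Protocol.** Criterion 9 in section 4.1 opens the treatment period by two routes.

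- Cohort A needs either CA-125 at or above twice the upper limit of normal (ULN) on two occasions, or low-volume disease on imaging with CA-125 above ULN. The imaging term reads: "Low volume radiological disease is defined as radiologically visible disease excluding intra-hepatic or intra-splenic metastases, ascites or pleural effusion thought to require drainage".
- Cohort B needs measurable disease within a size limit, "whatever serum CA-125 level and for whom further treatment is not planned within 2 months".

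Exclusion 7 in section 4.2 bars "Measurable disease associated with the appearance of symptoms justifying initiation of further treatment". On allocation, section 9.1.2 states: "Patients will be enrolled in separate cohorts at the time of treatment initiation according to" the two definitions. Section 9.3.2 then assigns a different endpoint to each: "Time to measurable relapse in Cohort A and Time to progression in Cohort B per RECIST 1.1".

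**SAP.** Section 2.1.2 repeats both cohort definitions. The treatment-period table in Appendix 1 does not:

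- EXCL07 rates RECIST 1.1 measurable disease as Major, with no condition on symptoms or cohort.
- INC10 (Major) describes relapse by the Cohort A routes only, with a threshold strictly above twice ULN.

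Section 6.1 defines the Evaluable Per-Protocol Set (EPP) as "all treated patients without any major protocol deviation who received at least 6 injections of TG4050", and section 6.2 removes any major deviator from it.

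**The concern.** Measurable disease is what defines Cohort B, yet the deviation list treats it as a Major breach. A patient enrolled exactly as the protocol intends would then be reported as wrongly included. INC10 adds a second breach for a Cohort B patient whose CA-125 is not raised, although the protocol accepts any level.

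At stake is what the report says about the quality of enrolment: Tables 14.1.1.3 and 14.1.1.4 and Listing 16.2.2.1 on deviations, and Table 14.1.1.2 on population counts. SAP 8.2.2 also asks for reasons for exclusion from each population. With so few patients, one false entry is conspicuous.

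The secondary issue is the cohort label itself. It decides which time endpoint a patient has in Listing 16.2.6.5 and where she sits in the by-cohort adverse event table (14.3.1.2). The two definitions are not mutually exclusive.

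**Working it through.** The plan states no sample size or power figure on this point, so there is nothing to reproduce. The check applies the written rules to each type of patient.

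**Inputs.** ULN = 35 U/mL (SAP 8.3.8), so 2 × ULN = 70 U/mL. Cohort rules are from protocol 4.1 and 4.2, codes from SAP Appendix 1. Six patients were treated (SAP 4).

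**Step 1: a Cohort B-eligible patient, by CA-125.** She is asymptomatic, has measurable disease within the size limit, and has no further treatment planned within 2 months.

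| CA-125 (U/mL) | Also meets Cohort A? | Protocol criterion 9 or exclusion 7 breached? | EXCL07 | INC10 |
|---|---|---|---|---|
| ≤ 35 | No | No | Major | Major |
| > 35 to < 70 | Yes | No | Major | No |
| ≥ 70 | Yes | No | Major | No |

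EXCL07 fires in 3 of 3 bands and INC10 in 1 of 3, against 0 of 3 under the protocol. Two of the 3 bands also satisfy Cohort A. The bands count definitions, not patients.

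**Step 2: does calling her Cohort A help?** No. EXCL07 has no cohort condition, so it still fires.

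**Step 3: number affected.** Let k be the number of the six treated patients who are in Cohort B. The documents do not give k, so its range is 0 to 6. At least k patients are major deviators by definition, and the EPP holds at most 6 − k.

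| k | 0 | 1 | 2 | 3 | 4 | 5 | 6 |
|---|---|---|---|---|---|---|---|
| k/6 | 0% | 16.7% | 33.3% | 50.0% | 66.7% | 83.3% | 100% |
| EPP at most | 6 | 5 | 4 | 3 | 2 | 1 | 0 |

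**Step 4: other Appendix 1 rows.**

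| Row | SAP Appendix 1 | Protocol 4.1 / 4.2 |
|---|---|---|
| EXCL01.1 | Neoadjuvant chemotherapy is Major | Criteria 4 and 7 provide for interval debulking and neoadjuvant patients |
| INC03 | Stage IIIC or IVA | Stage IIIC or IV |
| EXCL10 | Immunosuppression not stopped 4 weeks before | 2 weeks before |
| INC10 | Above 2 × ULN | At or above 2 × ULN |

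The INC10 threshold matters only at the boundary. A patient with no visible disease and exactly 70 U/mL twice meets the protocol and breaches the code. None of these four differences is specific to Cohort B.

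**Step 5: event wording.** SAP 7.6.2 runs from first injection to relapse or documented progression, and censors if there is no progression. SAP 8.8 runs from C1D1 to the first recurrence seen on imaging, and censors if there is no recurrence; its whichever-comes-first clause has only one event to choose from. Both cite RECIST 1.1, start at first dosing and censor at the last evaluable tumour assessment. Neither labels a rule for time to progression in Cohort B.

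**The case against.** The case for giving this little weight is substantial.

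- **Codes may not be applied mechanically.** SAP 8.5.1 summarises eligibility deviations collected in the eCRF, section 6.2 calls the Appendix 1 list non-exhaustive, and a data review meeting precedes lock (7.2). This stands as a limit on impact. It does not remove the conflict: a list that may be extended still contains the codes printed in it.
- **Little depends on the EPP.** The SAP document history records that EPP tables and listings were removed, and section 10 lists no EPP output. This stands; what remains is a population count and the reasons for exclusion.
- **The allocation intent is readable.** On small measurable lesions, protocol 3.3 says: "This patient population may benefit from study treatment and will be evaluated separately in Cohort B". An endpoint named time to measurable relapse presupposes that Cohort A has no measurable disease at entry, and the cohort is set at treatment initiation. This largely stands. It is rationale rather than an allocation rule, but it points to Cohort B.
- **A rule may exist out of sight.** The design figures are not shown and part of SAP 6.2 is redacted, so a precedence rule there cannot be excluded.

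A reader might go further and infer that the primary safety results are compromised, that cohort allocation was arbitrary, or that the two event wordings give different results. The documents support none of these. Safety is analysed in all treated patients whatever their deviations. Each patient should carry one label from treatment initiation. The wording difference is mostly editorial: a lesion known before first dosing cannot sensibly be the event.

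**Conclusion.** The concern holds as an inconsistency between SAP Appendix 1 and the protocol supplied. EXCL07 and INC10 contradict criterion 9 and exclusion 7, and they also contradict the Cohort B definition in SAP 2.1.2. If the codes are applied as written, all Cohort B patients are major deviators and none can be in the EPP. The fault extends to at least EXCL01.1, INC03 and EXCL10, so it is not only a Cohort B matter.

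Its size is limited. SAP 4 records: "The study was stopped due to low inclusion rate in October 2024 with 6 patients treated". With the cohort split unknown, the number affected lies anywhere from 0 to 6. That range does not estimate how many were miscoded; it shows only that each miscoded patient moves the deviation rate by 1/6, or 16.7 percentage points. Pooled safety does not change.

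The cohort overlap is real for patients with measurable disease within the Cohort B limit and CA-125 above ULN, but it is secondary. It rests on the visible text only.

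**What to change.** 1. **Appendix 1.** Before deviations are classified, reconcile every eligibility row with the current protocol criteria, by cohort, starting with EXCL07 and INC10. Enrolment under the Cohort B definition should not in itself count as a major deviation. Where a row and the protocol differ on a clinical rule (stage, prior chemotherapy, washout, CA-125 threshold), the passages must be reconciled by those responsible; this review does not choose between them.
2. **Cohort label.** Keep the cohort recorded at treatment initiation as the analysis label. In Listing 16.2.6.5, add baseline RECIST 1.1 measurability and baseline CA-125, and flag patients who meet both definitions.
3. **Event wording.** Use one event and censoring text in SAP 7.6.2 and 8.8, count only events after first injection, and state that the 7.6.2 formula also serves time to progression in Cohort B. Keep the endpoint assigned by cohort, as in protocol 9.3.2. Reassigning it by baseline measurability would change a secondary endpoint of an open-label study after it had stopped.

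**Cost.** A small SAP edit and a few listing columns from data already collected; no patient is relabelled. The downsides are that the edit comes after the study stopped, so it should be dated and explained, and that the flag shows the overlap without removing it. By-cohort results still need cautious reading.
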